7.2.5.8. Vitiligo-Specific Health-Related Quality-of-Life Instrument

VitiQoL is a 15-item quality-of-life assessment that asks participants to rate various aspects of their condition during the past month. Each item is scored on a 0 ("not at all") to 6 ("all of the time") continuous bipolar scale ([Lilly et al 2013](#)).

Scores are pooled and reported for each of the following 3 domains:

- Participation limitation (Item 3, 4, 6, 9, 10, 11, and 14);
- Stigma (Item 1, 2, 5, 7, and 15);
- Behaviors (Item 8, 12, and 13).

A total score ranging from 0 (better) to 90 (worse) will be also provided.

No imputation will be performed for missing values.

7.2.5.9. Hospital Anxiety and Depression Scale

HADS is a 14-item questionnaire that assesses the levels of anxiety and depression that a person is currently experiencing (Zigmond and Snaith 1983). There are 7 questions each for measuring anxiety and for measuring depression, with 4 possible responses to each question (responses are scored as 0, 1, 2, or 3). Separate total scores are calculated for anxiety and depression, each total score being the sum of the 7 questions. If 4 or more scores are missing (out of the 7) for anxiety or depression, the total score will be set to missing; otherwise, the total score will be the average score of the nonmissing items multiplied by 7.

7.3. Analysis of the Primary Efficacy Parameter

The primary efficacy endpoint is F-VASI75 at Week 24.

7.3.1. Primary Efficacy Analyses

The primary analysis will be based on the FAS population. The primary alternative hypothesis (superiority of ruxolitinib 1.5% BID compared with vehicle) will be tested using exact logistic regression (Mehta and Patel 1995). This model will include the treatment group (1.5% BID and vehicle) and stratification factors (skin type and region). The unadjusted p-values between each treatment group versus vehicle will be compared with the procedure defined in Section 3.2.

Odds ratio in response rates (ruxolitinib cream vs vehicle) at Week 24 will also be computed. All participants who are missing the F-VASI assessment at a given visit in the DB period will be handled using MI under the missing-at-random assumption. Rescue therapy is not allowed in the studies. Any participant who received rescue therapy will be considered as a protocol violation and will be imputed as a nonresponder. The numerical values for F-VASI will not be included in the MI model or other sensitivity analyses.

For MI, a fully conditional specification method (van Buuren 2007) that assumes the existence of a joint distribution for all variables will be used to impute F-VASI score. A regression model including treatment group, stratification factors, and baseline and postbaseline F-VASI scores up to Week 24 will be specified for the fully conditional specification method. The randomization seed will set to be 18424306 for Study INCB 18424-306 and 18424307 for Study INCB 18424-307. The imputation will be repeated 10 times to generate corresponding complete datasets, in order to reflect the uncertainty around the true value. After the missing values have been imputed, the binary variable F-VASI75 response will be derived. The exact logistic regression will be applied to each imputed dataset, and then the results will be combined for the inference.

The following is example SAS code for MI:

```
proc mi data=mi_wide seed=18424306 n impute=10 out=impute_fvasi;
  class trt01p strat1 strat2;
  var trt01p strat1 strat2 avalBASELINE avalWEEK4 avalWEEK8
  avalWEEK12 avalWEEK18 avalWEEK24;
  fcs;
run;
```

The following is example SAS code for exact logistic regression:

```
proc logistic data=fvasi75_mi exactonly;
  class trt01p (ref='VEHICLE CREAM') strat1 strat2/param=ref;
  model resp (event='Y') = trt01p strat1 strat2/covb;
  exact trt01p/estimate=both;
  by _Imputation_;
run;
```

The primary endpoint will also be examined for the PP population using the same model as the primary analysis.

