5.5. Replacement of Participants

Participants will not be replaced during the study.

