6.5.2. Criteria for Permanent Discontinuation of Study Drug Due to an Adverse Event

The occurrence of unacceptable severity of an AE not caused by the underlying disease will be presumed to be related to study drug treatment and will require that the study drug be permanently discontinued. Unacceptable severity is defined as follows:

[figure not shown]
- Occurrence of an AE that is related to treatment with the study drug that, in the judgment of the investigator or the sponsor's medical monitor, compromises the participant's ability to continue study-specific procedures or continuing treatment is considered to not be in the participant's best interest.
- Worsening of vitiligo that requires treatment with a prohibited concomitant medication.

[figure not shown]
See Section 7 for discontinuation procedures.

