10.3.1. Efficacy Analyses

10.3.1.1. Primary Analysis

The primary analysis will be based on the intent-to-treat population. The primary alternative hypothesis (superiority of ruxolitinib cream 1.5% BID compared with vehicle) will be tested using exact logistic regression ([Mehta and Patel 1995](#)). This model will include the treatment group (1.5% BID and vehicle) and stratification factors. The p-value for between-treatment

group testing will be compared with 0.05. Odds ratio and corresponding 95% confidence interval will be provided for comparing ruxolitinib cream and vehicle group at Week 24.

All nonresponders in the double-blind treatment period, as well as all participants who discontinue study treatment at any time before the timepoint of interest, or discontinue from the study for any reason, will be defined as nonresponders for the nonresponder imputation analysis.

Analysis will also be performed in the PP population for the primary endpoint. The following deviations are considered major:

- Missing primary endpoints on F-VASI;
- Compliance less than 60% based on the application numbers.

Participants with 1 or more such deviations will be excluded from the PP population. In addition, Protocol deviations related to inclusion/exclusion criteria, discontinuation criteria, and use of excluded concomitant medications will be evaluated and decided whether they should be excluded. Any exclusion from the PP population will be decided prior to breaking the blind.

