3.3. Sample Size Considerations

Approximately 300 participants will be randomized 2:1 to ruxolitinib cream 1.5% BID or vehicle and stratified by baseline skin type (Fitzpatrick scale Type I and II vs Type III, IV, V, and VI) and region (North America or Europe). The sample size is calculated to provide sufficient power ($> 85\%$) to detect a difference between the 1.5% BID with the vehicle in primary and key secondary endpoints. The powers for different endpoints are provided in [Table 2](#). The Fisher's exact test with a 2-sided alpha of 0.05 is used to provide a conservative evaluation of statistical power, and it is accurate when there is a small expected number of responders in the vehicle group.

Table 2: Powering for Primary and Key Secondary Endpoints

Endpoints	Response Rates in Ruxolitinib 1.5% BID ^a	Response Rates in Vehicle ^a	Power ^b
F-VASI75 at Week 24	20%	5%	95%
F-VASI50 at Week 24	30%	10%	95%
F-VASI90 at Week 24	10%	1%	88%
T-VASI50 at Week 24	10%	1%	88%
Vitiligo - VNS Response at Week 24	10%	1%	88%

^a Based on the results from a Phase 2, randomized, dose-ranging study (INCB18424-211).

^b Based on the Fisher's exact test with a 2-sided alpha of 0.05.

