7.4. Analysis of the Key Secondary Efficacy Parameters

If the primary objective is achieved, the statistical hypotheses for the following key secondary endpoints will be tested in a fixed sequence in the following order:

- F-VASI50 at Week 24
- F-VASI90 at Week 24
- T-VASI50 at Week 24
- Vitiligo – VNS Response at Week 24
- Percentage change from baseline in F-BSA at Week 24.

Key secondary efficacy analyses at Week 24 will be conducted in the FAS population. The statistical comparisons for binary outcomes (F-VASI50/90, T-VASI50, and VNS response) will be analyzed using the similar method as specified in the primary analysis.

For F-BSA, the missing values at Week 24 will be imputed using the MI method specified in the primary analysis. Then the derived percentage change from baseline in F-BSA at Week 24 will be analyzed using an ANCOVA model with treatment group, stratification factors, and baseline value as covariates. A test for superiority between ruxolitinib cream 1.5% BID and vehicle cream will be performed using the least squares mean estimate of the percentage change from baseline in F-BSA at Week 24 from the ANCOVA model. Superiority will be established if the p-value of the difference (ruxolitinib cream 1.5% BID minus vehicle) is < 0.05.

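### Nonresponse is triggered by receipt of rescue therapy, but the protocol stops study drug on need for it, so the same treatment failure can be scored in different ways at Week 24

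*SAP*

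**What the plan says.** SAP 7.3.1 gives one route to nonresponse that does not depend on the score: "Any participant who received rescue therapy will be considered as a protocol violation and will be imputed as a nonresponder". Every other missing F-VASI in the double-blind period goes to multiple imputation (MI) under MAR. The imputation model holds treatment group, stratification factors, and baseline and postbaseline F-VASI. It has no term for stopping study drug or for the reason.

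Protocol 6.5.2 lists, among the events that require permanent discontinuation of study drug, "Worsening of vitiligo that requires treatment with a prohibited concomitant medication". Protocol 7.1.2 then provides an EOT visit and a safety follow-up, and asks for the primary reason to be entered in the eCRF. It schedules no return at Week 24.

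Protocol 10.3.1.1 had a wider rule: "all participants who discontinue study treatment at any time before the timepoint of interest, or discontinue from the study for any reason, will be defined" (the status it assigns is nonresponse). SAP 10.1 openly replaces nonresponder imputation (NRI) with MI for the primary and key secondary endpoints, and makes no exception for stops driven by the outcome.

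For the continuous gated endpoint, SAP 7.4 says: "For F-BSA, the missing values at Week 24 will be imputed using the MI method specified in the primary analysis". It does not say what happens to an F-BSA value observed after prohibited therapy.

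**The concern.** The SAP already treats turning to other vitiligo treatment as failure, but it ties that to receipt, whereas the protocol acts on need. A participant whose site stops the cream as 6.5.2 requires may therefore be imputed, while one who takes the same treatment against the protocol is a nonresponder. Stopping because the disease worsened is not an incidental loss. If the recorded facial scores do not yet show the worsening, MAR imputation gives such participants roughly their arm's chance of response. With similar stopping rates in both arms, that widens the difference on the primary and gated binary endpoints.

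**Working it through.** **1. The plan's own figure.** SAP 3.3 gives about 300 participants at 2:1 (200 and 100), F-VASI75 rates of 20% and 5%, Fisher's exact test at two-sided 0.05, and power of 95%. Full enumeration gives 96.6%; variants and approximations run from 94.4% to 96.4%. The stated figure stands. The sample size section states no dropout allowance, and Protocol 5.5 says "Participants will not be replaced during the study". The share stopping for worsening is therefore an assumption.

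**2. One clinical event, several scores for F-VASI75.**

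| Before Week 24 | Handling |
|---|---|
| Takes prohibited treatment while on study drug | Nonresponder (SAP 7.3.1) |
| Stops drug on need; treatment starts and is recorded within 30 days of last dose (Protocol 6.6) | Nonresponder on a plain reading; SAP does not say whether it counts |
| Stops drug on need; no such treatment recorded; EOT1 not mapped to Week 24 | Missing, so MI under MAR |
| As above, but early EOT1 mapped to Week 24 | Observed value used |

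The last two rows are both open because EOT1 shares the Week 24 column in Protocol Table 3, EOT data go on their own eCRF page (Protocol 8.7), and the SAP has no visit-mapping rule.

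**3. Upper bound on the primary difference.** Let fA and fV be the shares stopping for this reason, and let everyone else respond at pA = 20% and pV = 5%. The upper bound used is imputation at the full arm rate. Difference under MI minus difference with stoppers as nonresponders = fA × pA − fV × pV. With fA = fV = f this is f × (20% − 5%):

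- f = 2%: 0.02 × 15 = 0.30 points
- f = 5%: 0.05 × 15 = 0.75 points (200 × 0.05 × 0.20 = 2.0 responders credited on ruxolitinib; 100 × 0.05 × 0.05 = 0.25 on vehicle)
- f = 8%: 0.08 × 15 = 1.20 points

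**4. Unequal stopping.** The expression is zero when fV = 4 × fA and negative beyond that. With fA = 2% and fV = 10%: 0.4 − 0.5 = −0.1 points, so scoring stoppers as nonresponders raises the difference from 15.0 to 15.1. With fA = 10% and fV = 2%: 2.0 − 0.1 = 1.9 points, and the difference falls to 13.1.

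**5. What MI does with recorded scores.** An illustrative simulation used assumed linear F-VASI courses, about 21% and 5% response, and stopping after Week 8.

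- Facial worsening on record at Week 8: MI makes about 1.5% of ruxolitinib stoppers and 0.5% of vehicle stoppers responders. At f = 5% that adds 0.05 × (1.5 − 0.5) = 0.05 points.
- Stopping unrelated to the facial score, for example worsening on the body: about 21% and 7%, close to the arm rates. At f = 5% that adds 0.05 × (21 − 7) = 0.70 points.

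**6. Power with stoppers as nonresponders** (same share in both arms, Fisher's exact): 96.2% at 2%, 95.5% at 5%, 94.1% at 10%.

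**7. Gated binary endpoints.** The same bound at the planned rates, for f = 2% to 8%, is f × (30% − 10%) = 0.4 to 1.6 points for F-VASI50, and f × (10% − 1%) = 0.18 to 0.72 points for F-VASI90, T-VASI50 and VNS. In the double-blind period VNS is scheduled only at Weeks 12 and 24, so an early stopper may have no VNS to condition on.

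**The case against.** The best defence is that MI conditions on each participant's own scores. A reader might infer that the SAP imputes these participants as if the cream had kept working. It does not: the assumption is that assigned treatment continued, given the F-VASI so far, and recorded facial worsening is then almost always imputed as nonresponse. This stands, and it confines the problem to worsening that the facial scores do not show.

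A reader might also infer that the protocol removes the participant, so that the rescue rule can never apply. The text does not go that far. Protocol 6.5.2 stops study drug, not participation; medications are recorded to 30 days after the last dose; and the SAP rule has no on-drug limit. The rule may still apply, but the SAP does not say so.

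The move from NRI to MI is disclosed with its reason, and NRI (7.3.3.1) and tipping-point (7.3.3.3) analyses are prespecified. The harshest tipping-point case, with all missing ruxolitinib participants failing and all missing vehicle participants responding, goes further than the change proposed here. That bounds the issue for F-VASI75. Both analyses sit under the primary endpoint, however, and SAP 7.4 names neither for F-VASI50, F-VASI90, T-VASI50 or VNS.

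The restricted-medications section (Protocol 6.6.2) is not in the text available for review, so the absence of a visible definition of rescue therapy is not counted against the plan.

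**Conclusion.** This is a cheap improvement, not a threat to the primary conclusion. The triggers in the two documents differ, and the protocol's wider rule on discontinuation was dropped without an exception for stops driven by the outcome. The same clinical failure can therefore be a nonresponder, an imputed value or an observed value.

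On the primary endpoint the upper bound is 0.3 to 1.2 percentage points. This rests on an assumed 2% to 8% stopping for this reason equally in both arms, the planned rates of 20% and 5%, and imputation at the full arm rate. Where facial worsening is already recorded, the effect is close to nil. A flat claim of bias toward ruxolitinib is not supported: the documents give no stopping rates by arm, and the sign reverses if vehicle stops for this reason more than four times as often. The gap matters more for the gated binary endpoints, which have no corresponding sensitivity analysis.

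**What to change.** In SAP 7.3.1 and 7.4, classify as a nonresponder for F-VASI75 and the gated binary endpoints any participant who, before Week 24, either

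- receives prohibited vitiligo therapy, including during follow-up after stopping study drug; or
- has worsening vitiligo or lack of efficacy as the recorded primary reason for discontinuing study drug.

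Keep MI for all other missing data. State how an early EOT1 value is mapped to a visit.

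For F-BSA, do not treat a value observed after prohibited therapy as an on-treatment result, and state how it is handled. Setting it to 0% change is unsuitable, because that could improve on a worsening that was actually observed.

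The passages on need for and receipt of prohibited treatment (Protocol 6.5.2, SAP 7.3.1) should be reconciled; no change to the clinical rule is proposed.

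The cost is SAP wording before unblinding, using the discontinuation reason that Protocol 7.1.2 already requires. The documents do not show the reason categories, so check that worsening and lack of efficacy can be identified. The downside is a slightly lower active response rate.

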In addition, sensitivity analyses, including MI and LOCF, may be performed. For MI, a fully conditional specification method ([van Buuren et al 2007](#)) that assumes the existence of a joint distribution for all variables will be used to impute F-VASI scores. A regression model including treatment group, stratification factors, and baseline and postbaseline F-VASI scores up to Week 24 will be specified for the fully conditional specification method. After the missing values are imputed, the binary variables will be derived based on the definition. The randomization seed will be set to 18424307 and the imputation will be repeated 10 times to generate corresponding complete data sets, in order to reflect the uncertainty around the true value. Exact logistic regression will be applied to each imputed dataset, and then the results will be combined for the inference. For LOCF, for the participants who discontinue study treatment at any time before the timepoint of interest or discontinue from the study for any reason, the last observed nonmissing value will be used to fill in missing values at the timepoint of interest. A tipping point analysis will be conducted to examine the potential effects of missing data. The missing binary response on F-VASI75 at Week 24 in each treatment group will be replaced by a range of values from the most conservative case to the most aggressive case. The most conservative case is that all the missing participants in active treatment groups are nonresponders and all the missing participants in the placebo group are responders, while the most aggressive case is the other way around. For each scenario, between-treatment comparisons will be performed using a chi-square test.

Subgroup analysis by baseline character, for example, skin type, age, and region, will be performed. Details will be provided in the Statistical Analysis Plan.

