3.2. Control of Type I Error

The gatekeeping testing strategy for the primary and key secondary analyses will be implemented to control the overall Type I error rate, 2-sided $\alpha = 0.05$. These endpoints will be tested in a fixed sequence at 2-sided $\alpha = 0.05$ level in the following order:

- Proportion of participants achieving F-VASI75 at Week 24
- Proportion of participants achieving F-VASI50 at Week 24
- Proportion of participants achieving F-VASI90 at Week 24
- Proportion of participants achieving T-VASI50 at Week 24
- Vitiligo – VNS Response at Week 24
- Percentage change from baseline in F-BSA at Week 24

The endpoint will be tested only if the primary endpoint (and the secondary endpoints in previous steps) are rejected.

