10.1. Changes to Protocol-Defined Analyses

- The FAS will be used to replace ITT in evaluation of the efficacy during DB period. The participants with only baseline but not any postbaseline assessments are excluded from the FAS. Those participants are not considered to be able to contribute to the efficacy analysis because of missing data in postbaseline visits.
- Multiple imputation will be used to replace the NRI to handle missing values in the analysis for primary and key secondary endpoints. Multiple imputation is able to provide unbiased estimates of the parameters under MAR.
- DLQI/CDLQI have been moved from exploratory endpoints to secondary endpoints.

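### Ten imputations leave avoidable seed noise in any borderline primary or key secondary p-value; raising the number to at least 100 costs little more than run time

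*SAP*

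**What the plan says.** SAP Section 7.3.1 imputes missing F-VASI by fully conditional specification, derives F-VASI75 and fits the model in each completed dataset: "The exact logistic regression will be applied to each imputed dataset, and then the results will be combined for the inference". The number is explicit: "The imputation will be repeated 10 times to generate corresponding complete datasets". The example code also uses 10. The seed is explicit too: "The randomization seed will set to be 18424306 for Study INCB 18424-306 and 18424307 for Study INCB 18424-307".

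SAP Section 10.1 gives this method its confirmatory role: "Multiple imputation will be used to replace the NRI to handle missing values in the analysis for primary and key secondary endpoints". Section 7.4 extends it to the other gated tests. The four binary endpoints "will be analyzed using the similar method as specified in the primary analysis", and for the last one: "For F-BSA, the missing values at Week 24 will be imputed using the MI method specified in the primary analysis". So all six gated tests use 10 imputations, five of them by reference. Under SAP Section 3.2 an endpoint is tested only if every earlier one was significant at two-sided 0.05.

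Protocol Section 10.3.1.1 (Amendment 3-US-CA) has the same count, "the imputation will be repeated 10 times to generate corresponding complete data sets", but there imputation is an optional sensitivity analysis for the primary endpoint. Among the gated tests, the protocol itself makes it the main method only for F-BSA (Section 10.3.1.2). I found no rationale for 10, no criterion for Monte Carlo error and no planned check with more imputations.

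**The concern.** With 10 imputations, the between-imputation variance is estimated from 10 values and the pooled estimate carries simulation error of its own. That error comes from the random number stream, not from the participants, and can be made as small as one likes by computing longer. If the result falls near 0.05, the reported p-value may land on either side depending on the seed.

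The fixed sequence adds to the cost. A miss at F-VASI90, for example, would block T-VASI50, VNS response and F-BSA. The SAP's alternative missing-data analyses (nonresponder imputation, last observation carried forward, tipping point; Section 7.3.3) cover the primary endpoint only, so the key secondaries have no planned cross-check.

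**Working it through.** **Inputs from the documents.** 200 vs 100 participants (about 300 at 2:1), two-sided 0.05, m = 10. SAP Table 2 states 95% power for F-VASI75 (20% vs 5%) and 88% for the 10% vs 1% endpoints.

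**Assumed inputs.** The documents give no missing-data rate. I took 5%, 10% and 20% dropout. Simulating a trial of this shape (five post-baseline visits, sequential regression imputation, responder status derived afterwards) gave a median fraction of missing information (FMI) of about 0.04, 0.08 and 0.15. A value of 0.25 is added as a stress case.

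**Step 1: the plan's own figure.** Exact enumeration of Fisher's test at 20% vs 5% gives 96.6% power, against 95% stated; this agrees within 2 points. For 10% vs 1% it gives 92.0%, against 88% stated. I use the stated powers below; they place results nearer the threshold.

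**Step 2: size of the noise.** With total variance scaled to 1, the Monte Carlo SD of the pooled z statistic is about √(FMI/m).
- FMI 0.08: √(0.08/10) = 0.089; √(0.08/100) = 0.028.
- FMI 0.15: √(0.15/10) = 0.122; √(0.15/100) = 0.039.

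A separate small direct simulation (12 datasets per level, F-VASI75 about 21% vs 5%) gave 0.104, 0.111 and 0.134 at 10%, 15% and 20% missing with m = 10, and 0.028, 0.037 and 0.037 with m = 100. The order of magnitude is the same.

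**Step 3: a borderline result.** Take a seed-free p of 0.04 (z = 2.054). By hand at FMI 0.08 and m = 10: 2.054 ± 1.96 × 0.089 = 1.88 to 2.23, or p from about 0.060 down to 0.026. Full Rubin pooling, with estimated between-imputation variance and t degrees of freedom, widens this slightly:

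| FMI | 95% seed range, m = 10 | Seeds with p < 0.05 | 95% seed range, m = 100 | Seeds with p < 0.05 |
|---|---|---|---|---|
| 0.04 | 0.029–0.055 | 91% | 0.036–0.044 | about 100% |
| 0.08 | 0.025–0.064 | 80% | 0.035–0.046 | 99.9% |
| 0.15 | 0.020–0.080 | 70% | 0.032–0.049 | 98% |
| 0.25 | 0.015–0.103 | 61% | 0.030–0.054 | 93% |

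(First row, m = 100: 2.054 ± 1.96 × 0.020 = 2.015 to 2.093.) A seed-free p of 0.001 stays significant with every seed. So does 0.01, except at FMI 0.25 (99.3% of seeds).

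**Step 4: how often this matters.** The chance that the decision differs from the seed-free one is about φ(z_power) × SD × √(2/π), where φ is the normal density, φ(1.645) = 0.103 at 95% power and φ(1.175) = 0.200 at 88%, and √(2/π) = 0.798.
- m = 10, FMI 0.15: 0.103 × 0.122 × 0.798 = 1.0%; 0.200 × 0.122 × 0.798 = 1.9%.
- m = 10, FMI 0.04 (SD 0.063): 0.5% and 1.0%.
- m = 10, directly simulated SDs (0.104–0.134): 0.9–1.1% and 1.7–2.1%.
- m = 100, directly simulated SDs (0.028–0.037): 0.2–0.3% and 0.4–0.6%.

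Two independent seeds disagree with each other somewhat more often. For FMI 0.04–0.15 and m = 10, simulation gives 0.8–1.8% of trials at 95% power and 1.5–3.4% at 88%, against 0.2–0.5% and 0.5–1.0% with m = 100. The average power loss from m = 10 is under 1.5 points even at FMI 0.25.

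**The case against.** The strongest reply is that this rarely matters. The wide ranges in Step 3 apply only once the result is already borderline; at the planned effects a change of decision is a 1–2% event per endpoint, and it goes in both directions. That stands, and it keeps the point minor.

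A reader might infer that the analysis could be steered through the seed, or that the error rate is inflated. The documents do not support this: one seed per study is written down in advance, so there is nothing to select.

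A reader might also infer that the 10% vs 1% endpoints, VNS above all because it has fewer visits to impute from, are the likeliest to land near 0.05. Their lower stated power does raise the chance, as Step 4 shows, but neither simulation modelled those endpoints. Fewer predictors may raise the FMI without placing a result near the threshold.

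The figures are also not those of the planned test. Section 7.3.1 specifies exact logistic regression and names no combining rule; I used a large-sample approximation. At a 1% vehicle rate the chance of no responder among 100 is 0.99^100 = 37%. The conditional odds ratio estimate is then infinite, with no finite standard error to pool, and more imputations would not cure that.

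Missingness may also be low: Protocol Section 2.4.2.2.3 describes few Phase 2 discontinuations. Against that, SAP Appendix A plans displays of assessments missed because of COVID-19. For the primary endpoint, the Section 7.3.3 analyses use no imputation seed and would help show fragility.

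**Conclusion.** The point holds as a cheap improvement of minor importance. Ten imputations add avoidable noise to six confirmatory p-values. The noise is harmless when a result is clear and uncomfortable when it is not: at a seed-free p of 0.04, between 9% and 30% of seeds would report non-significance for FMI 0.04–0.15. The issue is reproducibility of a borderline result. It is not bias, inflated type I error or a material loss of power, and it would be wrong to say that the seed decides the trial.

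The size rests on assumed missingness of 5–20%, the FMI values simulated from it and a large-sample test statistic. A higher FMI would widen the ranges; a lower one would narrow them.

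**What to change.** Before unblinding, set the number of imputations to at least 100 in SAP Section 7.3.1 and its example code, and state the same number outright in Section 7.4 for all five key secondary endpoints. If missingness proves high, 200 is safer: at FMI 0.25 and a seed-free p of 0.04, 98% of seeds then give p < 0.05, against 93% with 100. Keep the prespecified seeds. Report the Monte Carlo error of each pooled estimate. List the difference from Protocol Section 10.3.1.1 in SAP Section 10.1.

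The cost is longer run time for the exact models fitted in each imputed dataset, plus one line in Section 10.1. No participants, visits or data are added, and the estimand, model and alpha are unchanged. The timing matters, because raising the number after seeing a borderline result would look post hoc.
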